4.13. Primary Efficacy Measure

The primary efficacy measure is the time to first occurrence (after randomization) of a composite of death from CV causes, nonfatal MI, or nonfatal stroke.

An independent Clinical Endpoints Committee (CEC) will adjudicate all primary endpoint events. The CEC Charter will contain the final detailed event definitions used for adjudication; however high level definitions of each primary endpoint event are provided below.

- 1) **Death from Cardiovascular Causes** will be defined as a death resulting from an acute MI, sudden cardiac death, death due to heart failure, death due to stroke, and death due to other CV causes. All cases in which the cause of death cannot be determined (that is, undetermined) will be included in deaths from CV causes.
- 2) **Myocardial Infarction (MI)**. The term MI will be used when there is evidence of myocardial necrosis (that is, changes in cardiac biomarkers or post mortem pathological findings) in a clinical setting consistent with myocardial ischemia. Myocardial infarction will include the following subtypes: spontaneous MI, PCI-related MI, coronary artery bypass grafting (CABG)-related MI, and silent MI.
- 3) **Stroke** will be defined as an acute episode of neurological dysfunction caused by a focal or global brain, spinal cord, or retinal vascular injury. Strokes will be classified as ischemic, hemorrhagic, or undetermined. Stroke disability, as measured using the modified Rankin scale, will be assessed at approximately 30 days after the diagnosis.

The analysis for the primary efficacy measure will be based on the ITT population.

4.13.1. Primary Analysis Model

The primary analysis model is a Cox proportional hazards regression model. The model includes treatment as a fixed effect.

4.13.2. Analysis of Primary Endpoint

The endpoint for the primary analysis is defined as the first occurrence after randomization of death due to a CV cause, nonfatal MI, or nonfatal stroke (adjudicated as such). Time-to-event analyses (Section 4.3.4) will be performed for the composite primary endpoint. Treatment comparisons will be based on the hazard ratio and its 95% CI from the Cox model.

Counts and proportions of patients who experience a primary endpoint event will be calculated. Person-years of follow-up for the primary endpoint, and the incidence rate, calculated by dividing the number of patients who developed the event during the study period by the event-specific person-years of follow-up, will be provided. The ARD for an endpoint will be calculated based on the difference in cumulative incidence between the 2 treatment groups at the end of the study period. The ARD and NNT (Section 4.3.4) will be calculated for the primary endpoint. An adjusted 95% CI for the hazard ratio (dulaglutide/placebo) from the Cox proportional hazards regression model will be provided.

The primary analysis at the conclusion of the trial will be a superiority comparison of dulaglutide versus placebo. If the superiority test fails, then a noninferiority test with a 1.3 margin will be performed. If the upper limit of the 95% CI is below 1.0 (after adjustment for interim looks), dulaglutide will be declared superior to placebo in reducing the incidence of CV events. If the upper limit of the adjusted 95% CI of dulaglutide versus placebo is above 1.0 but below 1.3, dulaglutide will be declared noninferior to placebo in its effects on CV events.

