4.3. Default Analysis Methods

A default analysis method will be defined for certain types of variables (for example, baseline continuous, baseline categorical and time-to-event) that will be commonly encountered in this study. If a specific analysis requires a methodology other than the default for that variable type, the methodology will be described in the appropriate sections of this SAP.

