4.3.4. Time-to-Event Analyses

Time-to-event analyses will be performed for each of the adjudicated outcomes. For each analysis, all adjudicated events in the locked database will be used.

Time-to-event variables will be analyzed using survival analysis methodology if the total number of outcomes is 10 or more. A Cox proportional hazards regression analysis, where the model only includes a fixed effect for treatment, will be used to derive the hazard ratio (dulaglutide/placebo) and the associated 95% CI. The between-treatment comparison will be based on the p-value from the Cox model. The proportional hazard assumption will be examined graphically. If not met, data will be analyzed using accelerated failure time models. Kaplan-Meier (KM) estimates of the survival curve for each treatment will be generated. The number and proportion of patients with the event will be provided, along with the between-treatment p-value. Tied event times will be handled by the Exact method.

If the number of outcomes is <10, survival analyses will not be performed. Instead, Fisher's exact test will be used and the summary statistics will include the number and proportion of patients with the event plus the between-treatment p-value.

For adjudicated outcomes, the incidence rate per 100 person-years of follow-up will be calculated for each treatment group. The numerator will be the number of patients with the event, and the denominator will be the event-specific total person-years of follow-up divided by 100. Total person-years of follow-up is the sum, over patients, of the time on study until the first outcome (first event time or censoring time). The absolute risk difference (ARD) will then be calculated by subtracting the incidence in the dulaglutide arm from that in the placebo arm. For some analyses, the number needed to treat (NNT) to prevent an additional event will be derived using the incidence rates, that is, $1/(\text{Placebo rate} - \text{dulaglutide rate})$. These analyses will be performed where documented in the SAP, and this statistic will only be derived if the p-value from the Cox model is statistically significant.

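### For the primary endpoint, the SAP puts the ARD on cumulative incidence but the NNT on person-year rates, so the NNT is neither a number of patients nor 1/ARD

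*SAP*

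**What the plan says.** **SAP 4.13.2 (primary endpoint).** The incidence rate divides "the number of patients who developed the event during the study period by the event-specific person-years of follow-up", with no scaling. The section then states: "The ARD for an endpoint will be calculated based on the difference in cumulative incidence between the 2 treatment groups". The time is given only as "between the 2 treatment groups at the end of the study period". The following sentence reads: "The ARD and NNT (Section 4.3.4) will be calculated for the primary endpoint".

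**SAP 4.3.4 (default for time-to-event outcomes).** The rate is per 100 person-years: "the denominator will be the event-specific total person-years of follow-up divided by 100". Next comes "The absolute risk difference (ARD) will then be calculated by subtracting the incidence in the dulaglutide arm from that in the placebo arm". The word there is incidence, not incidence rate, but the sentence follows directly on the rate definition. For the NNT there is no such looseness: "the number needed to treat (NNT) to prevent an additional event will be derived using the incidence rates", with the formula written out as one over the placebo rate minus the dulaglutide rate, and only when the Cox test is significant.

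**SAP 4.3 (how defaults give way).** "If a specific analysis requires a methodology other than the default for that variable type, the methodology will be described in the appropriate sections" of the SAP.

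**Protocol 12.2.8.** The incidence rate is events over person-years, the ARD is the difference between arms in incidence, and the NNT is the reciprocal of that ARD, again only after a significant Cox result.

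**Secondary endpoints.** SAP 4.14 calls for an NNT for every secondary analysis with a significant Cox result. SAP 4.14.1 withholds it from the analyses of all deaths and of deaths by cause.

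**The concern.** A cumulative-incidence difference is a proportion tied to a follow-up time. A rate difference is events per unit of person-time. Adjacent sentences of 4.13.2 assign the primary ARD to the first and then point to a section built on the second. Two readings are possible, and each leaves something unsatisfied:

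- If the specific ARD sentence overrides the default, as SAP 4.3 suggests, the ARD is a cumulative-incidence difference. The NNT stays on rates, because 4.13.2 offers no other formula. The two reported measures are then not reciprocals, although the protocol says they are.
- If the pointer to 4.3.4 governs both measures, ARD and NNT are both rate-based and reciprocal, as in the protocol. The cumulative-incidence sentence then has no effect.

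No text gives the NNT a unit. Readers usually take an NNT as a number of patients, which the SAP formula does not produce. If the question stays open until the programs are written, the scale of a headline effect measure could be chosen with unblinded data in view.

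**Working it through.** **Inputs.** Placebo event rate 2.0% per year (SAP 4.1, protocol 12.1); hazard ratio 0.82 (same sections) and 0.85 (protocol 12.2.2); average follow-up about 6.5 years (protocol 7.1); dropout 0.15% per year (SAP 4.1). Constant hazards are assumed. The documents state no numerical ARD or NNT.

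**Step 1: reproduce the plan's own figure.** Events for 90% power at hazard ratio 0.82 and two-sided 0.05, by the Schoenfeld formula with 1:1 allocation:

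4 × (1.960 + 1.282)² / (ln 0.82)² ≈ 1067, or 1068 rounded up. SAP 4.1 states 1067.

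With 3 years of uniform accrual, 8 years maximum follow-up and the stated dropout, the sample size comes to about 9,534 to 9,634, against 9600 stated. The planning rates are therefore a sound basis for the comparison.

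**Step 2: rate scale, the SAP 4.3.4 formula.** NNT = 1/(placebo rate − dulaglutide rate).

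- Hazard ratio 0.85: rates 0.020 and 0.017 per person-year; 1/0.003 = 333 person-years. With rates per 100 person-years, 1/(2.0 − 1.7) = 3.3 hundred person-years, the same quantity.
- Hazard ratio 0.82: rates 0.020 and 0.0164; 1/0.0036 = 278 person-years, or 2.8 hundred.

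**Step 3: cumulative-incidence scale, the SAP 4.13.2 sentence.** ARD(t) = exp(−dulaglutide rate × t) − exp(−placebo rate × t), with t = 6.5 years.

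- Hazard ratio 0.85: exp(−0.1105) − exp(−0.130) = 0.01729; 1/ARD = 57.8.
- Hazard ratio 0.82: exp(−0.1066) − exp(−0.130) = 0.02079; 1/ARD = 48.1.

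| | HR 0.85 | HR 0.82 |
|---|---|---|
| Rate difference per 100 person-years | 0.30 | 0.36 |
| 1/(rate difference), person-years | 333 | 278 |
| Cumulative-incidence difference at 6.5 years | 1.73% | 2.08% |
| 1/ARD, patients over 6.5 years | 58 | 48 |

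**Step 4: can one be turned into the other?** Dividing person-years by the average follow-up gives 333/6.5 = 51 and 278/6.5 = 43, not 58 and 48. Rescaling does not make the NNT the reciprocal of the cumulative-incidence ARD.

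**Step 5: sensitivity at hazard ratio 0.82.** Reading 2.0% as an annual probability gives 275 against 48. Using a crude proportion at 6.5 years, with 0.15% annual dropout, gives 1/ARD of 48.3 in place of 48.1.

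**The case against.** The strongest reply is that the NNT is not in doubt. SAP 4.3.4 writes the formula out, 4.13.2 redefines only the ARD, and the default stands where no section replaces it. Protocol 12.2.8 builds its ARD after person-year rates, so its reciprocal gives the same value as the SAP's NNT formula. A figure of 58 appears only if the protocol's reciprocal is joined to the SAP's cumulative-incidence ARD. On this view the SAP simply reports two different summaries. Because 4.3.4 says only incidence for the ARD, 4.13.2 may be read as clarifying which incidence is meant.

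Much of this stands, and it narrows the point. It does not remove it. The literal SAP still reports an ARD and an NNT that are not reciprocals, contrary to the relation in the protocol, and gives the NNT no unit.

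Several stronger conclusions might be inferred and are not supported:

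- *That the plan allows three rival NNTs of 333, 3.3 and 58.* The first two are one quantity in two units.
- *That benefit would be misstated several-fold.* That needs the NNT to be printed without a unit and then misread as patients. The documents do not say that it will be.
- *That the undefined study end alone moves 1/ARD from 66 to 50.* Those values (hazard ratio 0.85) assume a fixed-time Kaplan-Meier estimate, read at 5.6 years and at 7.7 years (5.6 minimum plus 2.1 years of enrollment). SAP 4.13.2 also plans crude proportions, which give one number per arm and need no fixed time. What is missing is the name of the estimator.
- *That every secondary endpoint inherits the conflict.* SAP 4.14 has no competing ARD definition, and 4.14.1 withholds the NNT from the mortality analyses.
- *That the SAP itself must record any departure.* Protocol 12.2.1 allows the SAP, the clinical study report, or both.

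**Conclusion.** The inconsistency is real and confined to reporting. Followed literally, the SAP gives a primary ARD in proportions of patients and a primary NNT in person-time per event prevented, while protocol 12.2.8 makes one the reciprocal of the other. Under constant hazards and the plan's own rates, the NNT formula and the reciprocal of the ARD give 333 person-years against about 58 patients at hazard ratio 0.85, and 278 against 48 at 0.82, taking 6.5 years as the horizon.

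The Cox test, alpha, power and event target are unaffected. The NNT appears only after a significant Cox test, and a reader can derive either measure from the planned counts, rates and Kaplan-Meier curves. A reader might infer that the primary conclusion is at risk; nothing in the documents supports that. This is a minor correction to reporting.

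**What to change.** Use one scale for the primary ARD and NNT.

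- **Smaller edit.** Align the ARD sentence in SAP 4.13.2 with the rate-based definition in 4.3.4 and protocol 12.2.8. Say incidence rate explicitly, fix one rate unit, and label the reciprocal as person-years per event prevented.
- **Alternative.** Keep the cumulative-incidence ARD, name its estimator and time point, set NNT to 1/ARD and report it with that horizon. Describe the departure from protocol 12.2.8, with its justification, in the SAP and/or the clinical study report.

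In either case, carry the chosen NNT definition and unit to the SAP 4.14 endpoints for which an NNT is reported. Also reconcile 4.14 (NNT for each significant analysis) with 4.14.1 (none for the mortality analyses).

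The cost is a few lines of SAP text and minor programming, with no change to the inferential plan. It should be settled before unblinding.

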4.13.3. Subgroup Analysis of Primary Endpoint

The effects of dulaglutide compared to placebo on the incidence of the composite primary endpoint events will be examined across the prespecified subgroups of interest listed in Section 4.3.5.

The clinically relevant baseline characteristics for exploratory subgroup analyses for the primary endpoint include: prior MI, prior history of stroke or transient ischemic attack (TIA), prior hospitalization for unstable angina, prior coronary revascularization, existing microalbuminuria (defined as a urine albumin/creatinine ratio (ACR) >30 mg/g and ≤300 mg/g) or macroalbuminuria (see Section 4.17.3), current smoker, hypertension, hyperlipidemia, aspirin use, beta-blocker use, calcium channel blocker use, ACE inhibitor or angiotensin receptor blocker use, diuretic use, and antithrombotic (nonaspirin antiplatelets, vitamin K antagonists, heparin, direct thrombin inhibitor, or other antithrombotics).

A risk-adjusted analysis will be performed using these baseline characteristics, the prespecified subgroups, and a multifactor proportional hazards model. The baseline characteristics remaining in the final multifactor proportional hazards model plus the prespecified subgroup variables will be used for subgroup analyses.

The risk-adjusted and subgroup analyses will be performed using the ITT population.

4.13.4. Sensitivity Analyses of Primary Endpoint

The time-to-event analysis for the primary endpoint will be repeated using the PP population, but NNT will not be calculated.

Randomization was stratified by site. To account for the stratification, a time-to-event analysis of the primary endpoint stratified by site will be performed as a sensitivity analysis.

4.13.5. Assessing the Impact of Missing Data on the Primary Endpoint Analysis

Vital status or status on the primary endpoint may not be available for patients who discontinued early from the study or patients who were lost to follow-up during the course of the study. Sensitivity analyses will be performed exploring the impact of missing data on the primary endpoint findings. Specifically, 2 analyses of the primary endpoint will be performed. The first analysis which is extreme, will assume that all such patients in the dulaglutide group have experienced MACE primary endpoint events at the time of their discontinuations from the study or their last contact dates if they were lost to follow-up, while such placebo patients did not experience an event and thus are censored at their corresponding times. The second analysis, less extreme, will assume that all these patients from both treatment groups have experienced primary MACE endpoint events at the time of their discontinuations from the study or their last contact dates if they were lost to follow-up.

4.14. Secondary Efficacy Measures

Secondary efficacy measures include time (after randomization) to:

- first occurrence of the composite microvascular endpoint of diabetic retinopathy
- requiring laser therapy, vitrectomy, or anti-VEGF therapy; development of clinical proteinuria, a 30% decline in eGFR, or need for chronic renal replacement therapy
- first hospitalization for unstable angina
- first occurrence of each component of the composite primary endpoint
- death
- first occurrence of HF requiring hospitalization or an urgent HF visit

The independent CEC will adjudicate all deaths and hospitalizations for HF or unstable angina. The CEC Charter will contain the final detailed event definitions used for adjudication; however, high level definitions for these endpoints are provided below.

- 1) **All Cause Mortality** will be defined as deaths from CV causes, deaths from non-CV causes (for example, pulmonary, renal, etc.) and deaths not attributable to a CV or non-CV cause (that is, undetermined).

- 2) **Heart failure requiring hospitalization** will be defined as new or worsening clinical symptoms and physical signs of HF that require hospitalization for additional/increased therapy. An **urgent HF visit** will be defined as an urgent, unscheduled office/practice or emergency department visit (requires clinical signs and symptoms of HF and need for additional/increased therapy).
- 3) **Hospitalization for unstable angina** will be defined as clinical symptoms of myocardial ischemia (new or worsening) that necessitates hospitalization and one of the following: new or worsening ST or T wave changes on electrocardiogram (ECG), evidence of myocardial ischemia on imaging, angiographic evidence of a lesion in a coronary artery responsible for symptoms, need for coronary revascularization procedure (PCI or CABG) during the hospitalization, AND no evidence of an acute MI.

For the composite microvascular endpoint, the following definitions will apply:

- 1) **Diabetic retinopathy requiring laser therapy** will be defined as use of laser therapy (photocoagulation) for the treatment of diabetic retinopathy.
- 2) **Vitrectomy** for the treatment of diabetic retinopathy will be defined as a surgical procedure to remove the vitreous gel from the inside of the eye, and silicone gas, oil or other fluid is injected to fill the space the vitreous once occupied.
- 3) **Anti-VEGF therapy** for the treatment of diabetic retinopathy will be defined as an intravitreal injection(s) of an anti-VEGF agent for the treatment of diabetic retinopathy.
- 4) **Clinical proteinuria (macroalbuminuria)** will be defined as an ACR >300 mg/g (>33.9 mg/mmol).
- 5) **Renal replacement therapy (RRT)** will be defined as chronic hemodialysis or
- 6) Peritoneal dialysis used as maintenance therapy in patients with end stage renal disease (ESRD), or renal transplantation.
- 7) **A sustained 30% decline in eGFR** will be based on a 30% reduction from the
- 8) Baseline value (Visit 3) in 2 consecutive calculations of postrandomization eGFR, using the modification of diet in renal disease (MDRD) equation.

Events of laser therapy, vitrectomy, anti-VEGF therapy, or RRT will be prospectively collected. Identification of clinical proteinuria will be based on reported laboratory data (and/or calculated if needed) and eGFR will be calculated using reported laboratory (serum creatinine) and clinical data.

An event of the composite microvascular endpoint is the first occurrence after randomization of an event of diabetic retinopathy requiring laser therapy, vitrectomy for the treatment of diabetic retinopathy, anti-VEGF therapy for the treatment of diabetic retinopathy, development of clinical

proteinuria (macroalbuminuria, see Section 4.17.3), a 30% decline in eGFR (see Section 4.17.3) from baseline, or need for renal replacement therapy.

Time-to-event analyses will be performed for each of the secondary efficacy measures including the individual components of the composite primary endpoint using the ITT population. The analyses of death from CV causes, nonfatal MI, nonfatal stroke, HF requiring hospitalization or hospitalization for unstable angina will be based on adjudicated events. The NNT statistic will be provided for each analysis provided that the p-value from the Cox model is statistically significant. The incidence rate per 100 person-years of follow-up will also be calculated for each type of event.

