### **12.2.8. Efficacy Analyses**

Analysis of the composite primary endpoint as well as detailed analyses of the components of death from CV causes, nonfatal MI, and nonfatal stroke, will be performed. Time-to-event analyses will be performed for the composite endpoint as well as for each of the components. Counts and proportions of patients who experience a primary endpoint event and each component event will be calculated. Person-years of follow-up, incidence rates, and absolute risk differences (ARD) will be provided. The incidence rate for an endpoint is calculated by dividing the number of patients who developed the event during the study period by the event specific person-years of follow-up. The ARD will then be calculated by subtracting the

incidence in the dulaglutide arm from that in the placebo arm. The number needed to treat (NNT) statistic will be calculated as the reciprocal of the ARD for each analysis provided that the p-value from the Cox model is statistically significant.

Similar analyses will also be performed for all secondary endpoints. The eGFR values will be calculated using the MDRD equation [ $eGFR \text{ (mL/min/1.73 m}^2\text{)} = 175 \times \text{standardized Scr}^{-1.154} \times \text{age}^{-0.203} \times 1.212 \text{ [if black]} \times 0.742 \text{ [if female]}$ ] (Levey et al. 2006)]. The percentage change from baseline in eGFR will be calculated using the post-randomization values and the values calculated at Visit 3 (randomization) as baseline, and compared to -30%. The outcome will be the 1st of 2 consecutive eGFR calculations that are <-30%.

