#### **12.2.9.4. Analysis of Laboratory Analytes**

Laboratory measurements collected at scheduled visits will be listed by patient by visit using all randomized patients. An additional listing will be presented for all laboratory measurements that are outside the SI units (International System of Units) normal range. Baseline for calcitonin, ALT, and hemoglobin A1c, will be Visit 1 and for serum creatinine, urine ACR and lipids will be Visit 3. All summary analyses will be based on the ITT population. Laboratory measurements that fall within a visit window will be associated with that visit. The laboratory measurement within the window that was taken closest to the visit date will be representative of that patient's lab value for that visit.

Unless otherwise specified, continuous laboratory measures will be analyzed using an ANOVA model on the rank-transformed data. The model includes treatment. Treatment group comparisons will be performed with no multiplicity adjustment. Categorical laboratory measures will be analyzed using Chi-square tests or Fisher's exact tests. For lipids (total cholesterol, LDL-C, HDL-C, triglycerides, and non-HDL-C) the summary analysis will be conducted based on the percentage change from baseline using an ANOVA model described above. The change from baseline will be used for the ratio of total cholesterol to HDL-C.

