4.3.1. Baseline Analyses

Measurements collected at Visit 3 will be considered the baseline values. If data from Visit 3 are missing, measurements from the screening/run-in period (between Visit 1 and Visit 3) will be used. If a patient has no information for a variable prior to randomization, data will not be imputed and the patient will not be included in the analysis. Baseline analysis for any particular variable will be conducted using all randomized patients with baseline data for that variable.

The default analysis method for continuous baseline variables will be an ANOVA model with only a fixed effect for treatment; however, in situations where the baseline variable will be expected to violate the assumption of normality, Wilcoxon's rank sum test will be used. Such situations will be appropriately identified throughout this SAP. Summaries for continuous variables will include descriptive statistics (that is, number of patients, mean, standard deviation (SD), sample size, median, 10th percentile, 90th percentile, and interquartile range).

Categorical variables will be compared between treatments using Pearson's chi-square test if the expected count is at least 5 in at least 80% of the cells; otherwise, Fisher's exact test will be used. Summary statistics for categorical variables will include sample size, number, and proportion of patients.

For the CSR, a baseline factor will be considered as a covariate for a covariate-adjusted analysis only if the baseline factor is both clinically and statistically significantly different between treatment groups.

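### The microvascular composite is analysed with a treatment-only Cox model; prespecifying adjustment for baseline urine ACR and eGFR is a cheap change that may recover power, by an amount the documents do not fix

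*SAP*

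**What the plan says.** SAP 4.14 defines the composite. Two of its components come from laboratory values: clinical proteinuria (ACR above 300 mg/g), and a 30% fall in eGFR from the Visit 3 value on two consecutive calculations. The others are retinal treatments and chronic renal replacement therapy. The analysis is given in one sentence, "Time-to-event analyses will be performed for each of the secondary efficacy measures", with no covariate named. The default in SAP 4.3.4 then applies: "A Cox proportional hazards regression analysis, where the model only includes a fixed effect for treatment". Protocol 12.2.8 agrees: after describing the primary analysis it says "Similar analyses will also be performed for all secondary endpoints".

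Baseline values are planned. Under Protocol 12.2.9.4 the baseline "for serum creatinine, urine ACR and lipids will be Visit 3".

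Two provisions could bring in covariates, and neither reaches this endpoint as a matter of plan:

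- SAP 4.3.1 admits a baseline factor to an adjusted analysis for the clinical study report "only if the baseline factor is both clinically and statistically significantly different between treatment groups".
- SAP 4.13.3 says "A risk-adjusted analysis will be performed using these baseline characteristics, the prespecified subgroups, and a multifactor proportional hazards model", and its list includes albuminuria, but that analysis is for the primary endpoint. Sections 4.14.2.2 and 4.14.4 do the same for nonfatal MI and nonfatal stroke. SAP 4.3.5 calls all of these exploratory.

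**The concern.** A patient who enters with ACR 200 mg/g is much closer to the 300 mg/g threshold than one who enters at 5 mg/g. The primary composite has no baseline value of its own outcome; this endpoint partly does. Baseline renal status will also vary widely, because Protocol 8.1 admits patients through albuminuria or eGFR below 60, and equally through prior MI or risk factors alone.

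In a Cox model, omitting a prognostic covariate moves the treatment hazard ratio toward 1 even when the arms are balanced on it. The imbalance rule in SAP 4.3.1 therefore looks at the wrong property: the power gain comes from prognostic strength, not from chance imbalance. The SAP already uses the principle elsewhere. Its repeated-measures model in 4.3.2 carries the baseline value, and so does the severe hypoglycemia rate model in 4.17.1.1.

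What is at stake is efficiency on a secondary endpoint that starts with no alpha of its own (SAP 4.3.6.1).

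**Working it through.** **1. Reproduce the plan's own figure.** No power is stated for this composite, so the method is checked on the primary endpoint (SAP 4.1: HR 0.82, two-sided 0.05, 90% power). Schoenfeld: d = 4(1.95996 + 1.28155)² / (ln 0.82)² = 42.030 / 0.039383 = 1067.2, against 1067 stated.

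**2. Inputs.**

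- From the documents: 9600 patients (SAP 4.1), 1:1 (SAP 4.4); minimum follow-up 5.6 years (Protocol 7.1); enrolment 2.1 years (Protocol Attachment 5), so a maximum of 5.6 + 2.1 = 7.7 years; two-sided alpha 0.048 at the final analysis (SAP 4.3.6.1), taken as the most this endpoint could receive.
- Assumed: placebo cumulative incidence, true (conditional) HR 0.87, and s, the SD of the baseline score on the log-hazard scale.

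**3. Formula.** Power = Φ(|ln HR| × √d / 2 − 1.977). The adjusted model uses 0.87. The treatment-only model uses the value its estimate converges to when a normal score with SD s is left out, found numerically. The event count d is the same for both.

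Example, incidence 20%, s = 0.75: √1814 / 2 = 21.296. Treatment only: 0.1303 × 21.296 − 1.977 = 0.798, power 78.8%. Adjusted: 0.1393 × 21.296 − 1.977 = 0.99, power about 83.9%.

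| Incidence | s | HR, treatment only | Events | Power, treatment only | Power, adjusted | Gain (points, unrounded inputs) |
|---|---|---|---|---|---|---|
| 10% | 0.5 | 0.8716 | 901 | 53.4% | 54.5% | 1.1 |
| 10% | 0.75 | 0.8741 | 902 | 51.8% | 54.5% | 2.8 |
| 10% | 1.0 | 0.8780 | 904 | 49.2% | 54.6% | 5.5 |
| 20% | 0.5 | 0.8733 | 1810 | 81.7% | 83.8% | 2.0 |
| 20% | 0.75 | 0.8778 | 1814 | 78.8% | 83.9% | 5.1 |
| 20% | 1.0 | 0.8840 | 1820 | 74.3% | 84.0% | 9.7 |

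Simulation at 20% incidence (400 trials of 9600 per setting) gave 82.5% against 83.3% at s = 0.5, and 74.5% against 82.8% at s = 1.0, with Monte Carlo error of about 2 points.

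**4. Range.** Over incidence 5 to 30%, HR 0.85 to 0.90 and s from 0.3 to 1.5, the gain at alpha 0.048 runs from 0.1 to 29 points. With adjusted power held at 80% and incidence 5%, it is 0.2 points at s = 0.3 and 0.5 at s = 0.5. At 20% incidence, HR 0.87 and s = 0.75, a smaller alpha gives 5.7 points (0.0336) or 7.4 points (0.0072).

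**5. Patients already above 300 mg/g.** Protocol 8.1 admits macroalbuminuria, and neither document says whether such a patient can still develop clinical proteinuria. If not, those with the highest ACR lose that component's risk and a straight line in log ACR fits badly.

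This was checked in simulated trials with ACR followed yearly. Assumptions: baseline log ACR SD 1.4 around a median of 15 mg/g, or SD 1.6 around 30 mg/g; within-person SD 0.6; drift 0.05 per year; treatment shift 0.12; HR 0.87 for the other components; alpha 0.048; 100 trials per setting. Two settings were run at each prevalence of macroalbuminuria.

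| Share with baseline ACR above 300 | Gain from linear log ACR, these patients left out | Same, kept but not at risk for proteinuria |
|---|---|---|
| 2.5% | about 8 and 4 points | 5.5 and 1.5 |
| 9% | about 13 and 5 points | 2.4 and 1.3 |

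A further run with these patients kept but not at risk gave about 1 to 2 points from the linear term alone, and about 3 to 8 once an indicator for baseline macroalbuminuria was added. If they instead count as events at their first high value, the gain is about 4 to 16 points. These runs are small and show direction and order of magnitude only.

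**The case against.** The strongest reply is that nothing here is in error. The treatment-only test is prespecified, protects type I error, and matches both the primary model and Protocol 12.2.8. An adjusted hazard ratio is conditional on baseline renal status, which is a different estimand. All of that stands, and it makes this an improvement rather than a correction.

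The covariates may also be weaker than they look. The eGFR component is already measured against each patient's own Visit 3 value, and none of the checks above models eGFR. The retinal components have no baseline counterpart in ACR or eGFR. ACR is measured locally, and spot urine is accepted. Each of these would lower s for the composite as a whole. They limit the expected gain but do not make it vanish.

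A reader might infer more than the documents support:

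- **That the endpoint loses several points of power.** The inputs that would settle this are not given. Even s = 0.75 yields only 2.8 points at 10% incidence.
- **That the choice decides whether a microvascular claim can be made.** After the primary endpoint, alpha passes to nonfatal MI, CV death and nonfatal stroke. Later weights are in a figure not shown, and being first in the list of objectives is not testing order.
- **That the baselines exist for every patient.** They are planned. SAP 4.3.1 foresees gaps and says "data will not be imputed and the patient will not be included in the analysis".

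**Conclusion.** The point holds as a cheap improvement. The composite is tested without its own planned laboratory baselines, no risk-adjusted model covers it, and the only other route for a covariate depends on observed imbalance. The cost in power is about 1 point or less with weak covariates or few events. It is about 5 to 10 points with placebo incidence near 20% and a baseline score SD of 0.75 to 1.0, at alpha 0.048 and a true hazard ratio of 0.87. Incidence, hazard ratio and score SD are assumptions, and the alpha this endpoint will receive cannot be read. The result also depends on how patients with ACR above 300 mg/g at entry are treated: if they cannot have the proteinuria component, a linear term alone may deliver little.

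**What to change.** In SAP 4.14, before unblinding:

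- State that the p-value for the microvascular composite comes from a Cox model with treatment, baseline log ACR, an indicator for baseline ACR above 300 mg/g, and baseline eGFR. Stratifying by baseline albuminuria category is an alternative to the indicator.
- Use the last value before randomization, with a missing-value indicator, so that the rule in 4.3.1 does not drop patients from the ITT analysis.
- Say how patients with baseline ACR above 300 mg/g count for the proteinuria component.
- Exempt this endpoint from the imbalance rule in 4.3.1.
- Keep the treatment-only hazard ratio as a supportive analysis.

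The cost is wording, using data already planned for collection. Protocol 12.2.1 allows changes of method that leave the protocol's principal features intact to be made in the SAP before unblinding. The one downside is that the main hazard ratio for this endpoint becomes conditional on baseline renal status, and the report should say so.
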